We will study older adults (age ≥ 55 yrs.) with mild to moderate AD (n=100) and their caregiver (n=100) randomized (1:1) to one of two intervention delivery strategies for increasing MPA; real-time group video conferencing (RGV) vs. enhanced usual care (EUC). All participants will be provided with an iPad® for intervention delivery, Fitbit for self-monitoring MPA, and will be asked to complete 150 min of MPA/wk. Dyads in the RGV arm will be asked to complete three 45 min sessions that include aerobic, resistance, and balance/coordination exercises delivered by a trained

health coach via Zoom® software on an iPad® during mos. 0-6, and 1 session/wk. during mos. 7-12 to groups of 5-8 dyads in their home. Dyads in the EUC arm, will be given an exercise plan to do own their own. Dyads in both arms will be provided with written materials regarding exercise and physical activity from the National Institute on Aging and will be asked to complete brief (15-20 min) FaceTime™ meetings (0-6 mos.= 2/mo.; 7-12 mos.= 1/mo.) with the health coach to discuss progress, provide support and receive additional guidance on how to increase MPA. Our primary outcome, MPA, will be assessed by accelerometer across the 6 mo. active intervention and total 18 mo. study (secondary outcome).

C. Sample size, statistical methods, and power calculation

We will recruit 100 adults with AD and their caregiver (100 dyads) at baseline to achieve adequate power to test both short-term (0-6 mos.) and long-term (0-18 mos.) effects of the intervention. Our power calculation, based on 21 measurements of MPA, 35 measurements of secondary and exploratory outcomes, a previously observed correlation of 0.22 between repeated measures, and a high attrition rate of ~20%, indicated that this sample size (≥ 42 /arm after attrition) would produce $\geq 80\%$ power to detect an anticipated difference of 10-min/d in MPA ($SD=30$ min/d; $f=0.17$) between adults with AD randomized to RGV and EUC during the active intervention (0-6 mos.). This sample size would also yield $\geq 81\%$ power to test a between-arm difference as small as $f=0.15$, e.g., 6 ± 30 min/d in MPA, during maintenance (7-12 mos.) and no contact (13-18 mos.).

D. Subject Criteria (See Vulnerable Populations appendix, if applicable):

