Health coach training/blinding/fidelity. Training. We currently have 3 health coaches with experience in delivering group exercise using video conferencing to adults with AD. If needed, new health coaches will be trained by Drs. [name] and [name], and will shadow an experienced health coach for a minimum of 3 mos. prior to delivering the intervention on their own. [name] will train health coaches on how to perform each exercise, the order of presentation of the exercises, and provide guidance on how to recognize and correct common mistakes in performing specific exercises. [name] will provide training regarding strategies for effective communication with adults with AD, i.e., speaking clearly and slowly, providing/repeating simple specific instructions (68), focusing on reassurance and empathy for each participant (69), and fostering interaction between participants with strategies to ensure the focus of the interactions is not on dementia (67). Blinding. The nature of this trial precludes blinding of the health coaches; however, investigators, data analysts and research assistants will be blinded to condition. Intervention fidelity. Recordings from all group exercise sessions (RGV only) and individual support sessions will be reviewed. [name] will compare recordings of both group exercise and support sessions with a check list of exercises/topics scheduled to be included in each session. Health educators covering <80% of scheduled content, or failing to deliver physical activity as prescribed, will receive additional training from [name], and will be dismissed if the problem recurs.

ASSESSMENTS

MPA. Primary outcome (Baseline (0 mos.)- 6 mos.)/Secondary outcomes (0-18 mos.)

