Schedule. MPA in adults with AD and their caregiver will be assessed at baseline (1 wk. prior to starting the intervention), 3, 6, 12, and 18 mos. Equipment. MPA/sedentary time will be assessed using an ActiGraph model wGT3x-BT tri-axial accelerometer (3.3 x 4.6 x 3.5 cm, wt. = 19 g., dynamic range \pm 8 g). The ActiGraph provides valid and reliable assessments of MPA/sedentary time in adults (70-73). Our group has used the ActiGraph in several trials in a variety of populations including adolescents (74) and adults with IDD (75), and in typically developing children (76, 77) and adults (78, 79). Protocol. There is a lack of consensus on the best protocols to collect, process, and score ActiGraph data (80-82). Thus, our decisions regarding ActiGraph location, monitoring period, data processing etc. were based on current practice, as described below. Participants will be asked to wear the ActiGraph on a belt over the non-dominant hip at the anterior axillary line during waking hours for 7 consecutive days, except for bathing and swimming. A 7-day monitoring period provides a reliable estimate of MPA (81, 83-85). The hip, rather than the wrist location, will be used due to the lack of comparable data and established protocols for assessment of MPA using wrist-worn ActiGraphs (86-88). ActiGraph distribution/reminders. Research staff will distribute and

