Statistical design. Baseline equivalence. The distributional properties of baseline demographic characteristics (MPA, BMI, age, sex, race/ethnicity, etc.) and dyadic relationship between adults with AD and their caregiver (quality, type, number of caregivers) will be inspected within the sample and between the RGV and EUC arms. Variables that demonstrate a significant nonequivalence between RGV and EUC arms will be statistically controlled in the hypothesis testing to improve accuracy of our inferences on intervention effects. Additionally, variables that significantly differ between dyads that dropped out and those that did not will be controlled to minimize any systematic bias stemming from attrition.

Primary aim: *To compare MPA (min/wk.) across the 6-mo. active intervention in adults with AD randomized to RGV and EUC.* Our analysis will account for/evaluate the clustering of observations (repeated measurements; level 1) within participants (level 2) and dyads (level 3; if multiple caregivers) by estimating intra-class correlations and variances/covariances of regression

coefficients at, and across, different levels in random-effects multilevel models (mixed models). To address the aim, models will examine overall between-arm difference in MPV across time (group effect), linear/non-linear change in MPV over time (time effect), and, if appropriate, between-arm difference in this change (group-by-time interaction), while controlling for (i) the number of contacts with research staff and (ii) the baseline characteristics imbalances between participant subgroups (RGV vs. EUC, dropouts vs. completers). For example, a significant interaction would indicate that adults with AD in the RGV arm achieve more minutes of MPA compared to those in the EUC arm and this difference becomes greater as intervention participation increases, i.e., in the later mos.

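### The 21 measurements in the power calculation appear to include the pre-intervention week; the ≥80% survives without it, but the primary contrast should exclude it, because pooling it into the group effect would cut power to about 51%

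*Combined protocol and SAP*

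**What the plan says.** Combined protocol and SAP, section C (Sample size, statistical methods, and power calculation): "Our power calculation, based on 21 measurements of MPA", then "35 measurements of secondary and exploratory outcomes", "a previously observed correlation of 0.22 between repeated measures" and "a high attrition rate of ~20"%. From these it derives at least 80% power, with at least "42 /arm after attrition", for 10 min/d (SD 30 min/d, f = 0.17) between adults with AD in the two arms during the active intervention, months 0-6. It does not say how 21 arises, and gives no significance level.

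ASSESSMENTS, MPA, Schedule: MPA "will be assessed at baseline (1 wk. prior to starting the intervention), 3, 6, 12, and 18 mos". Each assessment is a 7-day wear period.

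ASSESSMENTS, MPA heading: "Primary outcome (Baseline (0 mos.)- 6 mos".

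V.A (Statistical and Data Analysis), Primary aim: "models will examine overall between-arm difference in MPV across time (group effect"), plus a time effect and, where judged appropriate, a group-by-time interaction. (MPV is read here as MPA.) Under Baseline equivalence in the same section, baseline MPA is one of the characteristics to be controlled if the arms differ significantly on it, or if dropouts differ significantly from completers. Nothing says whether the baseline week is otherwise an outcome row in the primary model or a covariate.

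**The concern.** In the 0-6 month window the schedule yields 21 daily values only if the baseline week is counted. That week precedes the intervention, so under randomisation its expected arm difference is zero, whereas the power calculation applies one difference of 10 min/d to all 21 measurements.

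The count itself changes little. What matters is whether the primary analysis treats the baseline week in the same way. If it is an outcome row and the primary test is the overall group effect, a third of the averaged data carries no effect and the estimate shrinks accordingly. The plan's text permits this and does not choose between it and contrasts that avoid it. The same trial and the same true benefit could therefore be tested with very different power, depending on a choice still open when the data arrive.

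**Working it through.** **Inputs.** From section C: difference 10 min/d, SD 30 (variance 900), correlation r = 0.22, 42 per arm. From the Schedule: 7 days at each of 0, 3, 6, 12 and 18 months. Assumed: two-sided 5% level; the same r between any two days, within or across weeks. Attrition of 20% from 50 per arm leaves 50 x 0.8 = 40, not 42, so both are shown.

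**Where 21 comes from.** Months 0, 3 and 6: 3 x 7 = 21. All five assessments: 5 x 7 = 35, the other count in section C. Post-baseline days in months 0-6: 2 x 7 = 14.

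**Formulas.** The mean of m days has variance V = 900 x [1 + (m - 1) x 0.22] / m. The arm difference has SE = sqrt(2V/n). Power is from the noncentral F with 1 and 2n - 2 df and noncentrality (difference/SE)².

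**1. The plan's figure: 21 days, 10 min/d on every day.** V = 900 x 5.40/21 = 231.4; SE = sqrt(2 x 231.4/42) = 3.32; noncentrality (10/3.32)² = 9.07; power 84.5% (82.7% at 40 per arm). This is consistent with the stated ≥80%.

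**2. Post-baseline days only: 14 days, 10 min/d.** V = 900 x 3.86/14 = 248.1; SE = 3.44; noncentrality 8.46; power 82.0% (80.1% at 40 per arm). Dropping the baseline week costs about 2.5 points, because at r = 0.22 further days on the same person add little.

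**3. Baseline week pooled into the group effect.** The average difference is (0 + 10 + 10)/3 = 6.67 min/d. SE is 3.32 as in step 1; noncentrality (6.67/3.32)² = 4.03; power 51.0% (49.0% at 40 per arm). To reach 80% on this contrast the true effect at 3 and 6 months would have to be about 14 min/d.

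**4. Group-by-time test with baseline as an outcome row.** The between-person part cancels. Day-to-day variance is 900 x (1 - 0.22) = 702, so each weekly arm difference has within-person variance 2 x (702/7)/42 = 4.78. Squared deviations of 0, 10, 10 from their mean sum to 66.7; noncentrality 66.7/4.78 = 13.96 on 2 df; power about 92%.

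**5. Baseline week as covariate.** Baseline-week mean: variance 900 x 2.32/7 = 298.3. Post-baseline mean: 248.1. Covariance: 900 x 0.22 = 198. Residual variance 248.1 - 198²/298.3 = 116.7; SE = sqrt(2 x 116.7/42) = 2.36; power 98.7% (98.3% at 40 per arm).

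| Handling of the baseline week | 42/arm | 40/arm |
|---|---|---|
| Counted, 10 min/d on all 21 days | 84.5% | 82.7% |
| Outcome row, overall group effect | 51.0% | 49.0% |
| Dropped, 14 days | 82.0% | 80.1% |
| Covariate, 14 days | 98.7% | 98.3% |

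**The case against.** A reader might infer that the ≥80% depends on an arm difference before treatment starts, that real power is 51%, and that 100 dyads is too few. The documents do not support that. Step 2 keeps the bound with no baseline days at all, and the sample size is unchanged.

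Nor does the plan commit to the analysis that gives 51%. Section C places the 10 min/d within the active intervention, which starts after the baseline week, and names no model term. The Primary aim text also provides for a group-by-time interaction, and its one illustration of a positive result is a significant interaction, which keeps high power (step 4). Listing MPA among the baseline characteristics suggests use as a covariate. The MPA heading may describe only an assessment window.

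The origin of 21 is also an inference. Section C attaches 35 to secondary and exploratory outcomes, most of which are assessed at four visits rather than five. The text on missing accelerometer data mentions seven week-long assessments where the Schedule has five; 7 x 7 = 49 matches neither count.

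All of this limits the claim, but an open choice remains. The overall group effect is the first term named, the interaction is conditional, and baseline MPA is controlled only if a significance test happens to flag it. No sentence keeps the baseline week out of the outcome rows.

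**Conclusion.** The point holds in limited form. The 21 very probably includes 7 pre-intervention days and should read 14. The corrected unadjusted power is about 82% at 42 per arm and 80% at 40, so the stated bound and the 100 dyads stand, with almost no margin at 40.

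The material issue is the undefined primary contrast. Under the plan's own inputs, power for the same true 10 min/d effect runs from about 51% (baseline pooled into the group effect) to about 98-99% (baseline as covariate). The 51% is conditional on that pooled reading; it is not the power of the trial as designed.

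These figures assume a two-sided 5% level, an equal effect at 3 and 6 months, and a correlation of 0.22 that is the same across weeks as within them. If days months apart correlate less than days within a week, the gain from the covariate will be smaller.

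**What to change.** - **Section C:** replace the 21 MPA measurements with 14 post-baseline measurements (7 days at each of 3 and 6 months). State the significance level. Restate unadjusted power as about 82% at 42 per arm or 80% at 40, and say which number per arm follows from the assumed attrition.
- **MPA heading under ASSESSMENTS, and Primary aim in V.A:** define the primary contrast as the RGV minus EUC difference in MPA averaged over 3 and 6 months. Include baseline MPA as a covariate in every case, not as an outcome row and not only when the arms look imbalanced. If the adjusted power is quoted (about 98-99%), state that it relies on the constant correlation.

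The cost is rewording in three places, made before the data are unblinded. No extra participants, visits or measurements are needed. Compared with the calculation as counted, the unadjusted figure falls by about 2.5 points, and the covariate more than recovers this under the plan's inputs.

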
Secondary outcomes. Secondary/exploratory outcomes will be assessed at baseline (1-2 wks. before starting the intervention), 6, 12 and 18 mos. in the adult with AD or caregiver's home. Our experience with similar trials suggests these assessments, which will be completed by trained staff blinded to condition, will require ~75 min to complete. Staff will receive refresher training and complete reliability assessments for all physical measures 2-3 times/yr.

Secondary outcomes-Adult with AD. Sedentary time will be assessed using data collected from the ActiGraph as described above. Functional fitness will be measured using Functional Fitness Test (FFT) previously called the Senior Fitness Test (92). The individual fitness test items involve common activities such as getting up from a chair, walking, lifting, bending, and stretching. Reliability of the FFT in older adults with cognitive impairment is high in all of the test items (ICC ≥ 0.93) (93). Activities of daily living will be assessed using the Disabilities Assessment for Dementia (DAD)(94). The DAD includes 40 items: 17 related to basic self-care and 23 to instrumental activities of daily living. DAD demonstrated a high degree of internal consistency (Cronbach's alpha = .96) and excellent inter-rater (n = 31, ICC = .95) and test-retest (n = 45, ICC = .96) reliability. In addition, it has been shown to have no gender bias. Quality of life will be assessed using the QOL-AD(95), a brief, 13-item self-report and 15-item caregiver-report. The QOL-AD has shown acceptable validity and reliability when completed by adults with AD or a caregiver proxy (ICC= .76 and .92 respectively) (95). Residential transitions, i.e., from home to institutional care, will be tracked by health coaches. We will also assess caregiver desire to institutionalize the adult with AD using the 6-item Morycz's Desire-to-Institutionalize Scale (96). This scale demonstrated moderate reliability with KR-20 alpha of .694 for Whites, .742 for African Americans, and .767 for Hispanics (97). Neuropsychiatric symptoms will be assessed using the Neuropsychiatric Inventory (NPI) (98). The NPI evaluates 12 neuropsychiatric disturbances common in dementia and the amount of caregiver distress engendered by each of the neuropsychiatric disorders. Validity

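### The stated ≥81% long-term power is not supported as written: it counts 35 whole-trial measurements for phases with one 7-day week each, and its 6 min/d example is f = 0.10, not 0.15

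*Combined protocol and SAP*

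**What the plan says.** Section C (Sample size, statistical methods, and power calculation) says that 100 dyads give adequate power for both short-term (0-6 months) and long-term (0-18 months) effects. The calculation is "based on 21 measurements of MPA", "35 measurements of secondary and exploratory outcomes", "a previously observed correlation of 0.22 between repeated measures" and attrition of about 20%, leaving at least 42 per arm. From this it claims at least 81% power for a between-arm difference as small as f = 0.15, with 6 ± 30 min/d of MPA as the example, "during maintenance (7-12 mos.) and no contact (13-18 mos".)

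The schedule is set elsewhere:

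- Under Assessments (MPA, Schedule), accelerometry is done at "baseline (1 wk. prior to starting the intervention), 3, 6, 12, and 18 mos", with 7 consecutive days of wear each time.
- Under Secondary outcomes: "Secondary/exploratory outcomes will be assessed at baseline (1-2 wks. before starting the intervention), 6, 12 and 18 mos".

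The Statistical and Data Analysis section compares the secondary outcomes, including MPA, across 18 months. It uses mixed models with group, time and group-by-time terms. It does not say which of these terms the 81% refers to.

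**The concern.** The 35 has no stated derivation. The one that fits the schedule is 5 assessments × 7 days, just as 21 is 3 × 7 for months 0, 3 and 6. It is therefore a whole-trial count. Of the 35 days, 21 come from baseline and the active phase, and 7 of those precede any treatment. The claim resting on it concerns months 7-12 and 13-18, and each of those phases has only one wear week, at its end. The wording also gives 35 measurements to secondary and exploratory outcomes in general, although fitness, daily living, quality of life, burden and cognition are measured at most four times.

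The effect size and its example also disagree. At SD 30, a difference of 6 min/d is not f = 0.15.

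The Rationale presents the 12-18 month effect as the open question. A null result at month 12 or 18 would be read against a claimed power of at least 81%. If the real power for the quoted difference is far lower, that result would be taken as evidence that nothing lasts when the design could easily have missed it.

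**Working it through.** **Inputs from the plan.** Correlation ρ = 0.22; SD 30 min/d; f = 0.15; example 6 min/d; 42 per arm (N = 84). Attrition of 20% gives 100 × 0.80 / 2 = 40 per arm (N = 80), so both are shown.

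**Assumed.** Two-sided alpha of 0.05, because the plan states neither alpha nor sidedness. Power is from the noncentral F with 1 and N − 2 degrees of freedom.

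**Formula.** For two equal arms, f = (difference / SD) / 2. The noncentrality is λ = f² × N / v, where v is the variance of the analysed summary in units of the daily variance. For the mean of m days, v = (1 + (m − 1)ρ) / m.

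**Step 1: the plan's figure.** With m = 35, v = (1 + 34 × 0.22) / 35 = 0.2423. Then λ = 0.0225 × 84 / 0.2423 = 7.80 and power is 78.8% (79.8% by normal approximation). With N = 80 it is 76.8%. The stated 81% is approximately reproduced, but as the power for an average group difference over all 18 months.

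**Step 2: the data in the named phases.**

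- One week, m = 7: v = (1 + 6 × 0.22) / 7 = 0.3314; λ = 5.70 at N = 84.
- Months 12 and 18 pooled, m = 14: v = (1 + 13 × 0.22) / 14 = 0.2757; λ = 6.85.

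**Step 3: change from the baseline week to one later week.** v = 2 × 0.3314 − 2c, where c is the correlation between days in different weeks.

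- If c = 0.22, v = 0.2229 and λ = 8.48.
- If c = 0.18 (an illustrative decay, not in the plan), v = 0.3029 and λ = 6.24.

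| Contrast, f = 0.15 | 42/arm | 40/arm |
|---|---|---|
| 18-month average, 35 days | 78.8% | 76.8% |
| Single week, 7 days | 65.5% | 63.4% |
| Months 12 and 18 pooled, 14 days | 73.5% | 71.3% |
| Change from baseline, c = 0.22 | 82.1% | 80.1% |
| Change from baseline, c = 0.18 | 69.5% | 67.3% |

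**Step 4: the quoted example.** f = (6 / 30) / 2 = 0.10. A value of f = 0.15 corresponds to 0.15 × 2 × 30 = 9 min/d. For a baseline-adjusted single week, v = 0.3314 − c² / 0.3314, which is 0.1854 at c = 0.22.

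| Contrast, f = 0.10, 42/arm | λ | Power |
|---|---|---|
| Single week | 0.01 × 84 / 0.3314 = 2.53 | 35% |
| All 35 days | 0.01 × 84 / 0.2423 = 3.47 | 45% |
| Change, c = 0.22 | 0.01 × 84 / 0.2229 = 3.77 | 48% |
| Baseline-adjusted, c = 0.22 | 0.01 × 84 / 0.1854 = 4.53 | 56% |

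None of these comes near 81%.

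**The case against.** The strongest reply is that 35 is the right count for the long-term analysis the plan describes. Section C defines long-term as 0-18 months, and the mixed model for MPA and sedentary time uses every accelerometer week. On that reading the power at f = 0.15 is 78.8%, close to the stated figure. This stands for the 18-month accelerometer average. It does not stand for the two phases to which the sentence attaches the 81%.

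The second reply is that the single-week figure discards earlier data, whereas the planned model has a group-by-time term. This also stands in part. Under an exchangeable 0.22, change from baseline gives 82.1% (42 per arm) or 80.1% (40 per arm), and a baseline-adjusted week gives 88.4% or 86.8%. But the plan names no such contrast, makes adjustment for baseline MPA conditional on observed imbalance, and does not say that correlation holds undiminished across 12-18 months.

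Three stronger readings are tempting and unsupported:

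- **That 81% at f = 0.15 cannot be reached.** The contrasts above show that it can, under an assumption the plan leaves unstated.
- **That the true detectable difference is 10-11 min/d.** That holds for a comparison of one week's means alone. The same ρ gives about 8.9-9.1 min/d for change.
- **That four-visit outcomes have 56% or 54% power.** That borrows 0.22, which appears to come from daily MPA data, for instruments whose repeated-measures correlation the plan does not give.

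**Conclusion.** The claim of at least 81% power during maintenance and no contact is not supported as written. The count behind it is a whole-trial count, and the contrast is not named. At f = 0.15 with 42 per arm, the contrasts tabulated above give 65.5% to 82.1%; the top value requires days months apart to correlate as strongly as days in the same week. A modest fall in that correlation, to 0.18, takes it to 69.5%.

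The mismatch between f = 0.15 and 6 ± 30 min/d is a separate error and does not depend on the measurement count. At the quoted difference, power is about 35% to 56% under every contrast checked. For the four-visit outcomes, the 35-measurement basis is wrong, and the documents do not supply what is needed to replace it with a power figure.

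These results assume two-sided alpha of 0.05 and the plan's SD and ρ. The primary 0-6 month calculation uses 21 measurements and is unaffected. The long-term comparison is secondary, so this should be corrected but does not threaten the main result.

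**What to change.** Rewrite the long-term part of the power paragraph so that it:

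- states alpha and sidedness, and names the contrast (18-month average, single-phase difference, or change from baseline);
- uses 7 daily values per phase, keeping 35 only for the 18-month accelerometer average;
- states the correlation assumed between days months apart, and gives the detectable difference that follows from that contrast and correlation;
- makes f and the min/d example agree (f = 0.15 is 9 min/d at SD 30; 6 min/d is f = 0.10);
- removes the 35-measurement basis and the power claim for four-visit outcomes, and presents those as estimates with confidence intervals.

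Neither 10-11 min/d nor 56%/54% should be inserted as a replacement figure, since each depends on a choice or a correlation the plan does not supply.

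The cost is one paragraph of text and probably a less favourable stated figure. No participants, visits or wear days are added.

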Removal from the Study. If the study present greater then minimal risk to a participant they will be censored from the study and referred to the University of Kansas Alzheimer's Disease Center for recommendations for other resources for PA. All participants and caregivers will be informed that they may be censored from the study due to safety risk during the consent procedure. We believe the following scenarios would present a greater than minimal risk to participants. Lack of caregiver. A caregiver will be asked to participate in the intervention with the adult with AD. Many caregivers will be older adults and it is possible some may become deceased, become ill or hospitalized and unable to provide care to the AD individual. If this happens, the adult with AD will be asked to identify another individual to serve as the official study caregiver. If an alternative caregiver cannot be identified the individual with AD will be censored from the study from that time forward.

Transition to a residential facility. Some adults with AD may be placed in a residential care facility during the 18-mo. intervention. If this occurs the adult with AD will be censored from the study.

Change in severity of AD. If dementia progresses to the point that either the caregiver or research staff feel the intervention is no longer safe for the individual, they will be censored from the study. If an individual with AD is removed from the study for one of the aforementioned reasons (transition to residential facility or change in severity of AD), decides to no longer participate in the intervention, or dies during the intervention, the caregiver will be allowed to continue in the intervention, if they choose. If a caregiver stays enrolled in the intervention without the person with AD we will no longer collect outcomes regarding Caregiver Burden or Quality of the dyadic relationship.

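### The floor of 42 per arm does not follow from about 20% attrition of 50 per arm (40 remain); active-phase power survives, but the later-phase 81% is not reproduced at f = 0.15

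*Combined protocol and SAP*

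**What the plan says.** All the figures are in the combined protocol and SAP.

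- **Recruitment.** Section C (Sample size, statistical methods, and power calculation): "We will recruit 100 adults with AD and their caregiver (100 dyads) at baseline".
- **Allocation.** Section B (Study Type and Design): participants are "randomized (1:1) to one of two intervention delivery strategies for increasing MPA", which makes 50 dyads per arm.
- **Attrition and retained number.** Section C assumes "a high attrition rate of ~20%, indicated that this sample size (≥ 42 /arm after attrition". It gives no derivation of 42 and does not say what period the rate covers.
- **Power.** The same paragraph claims at least 80% power in the active phase (0–6 months) for 10 min/d with SD 30 (f = 0.17). It also claims at least 81% at f = 0.15 for maintenance and no contact. The inputs are 21 measurements of MPA, 35 of secondary and exploratory outcomes, and a correlation of 0.22 between repeated measures. Alpha, sidedness and the power formula are not given.
- **Dropouts in the analysis.** The missing-data paragraph of the data analysis section keeps dropouts' partial data through full information maximum likelihood (FIML).

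**The concern.** The retained number is written as a floor, and the attrition rate beside it is called high. A cautious allowance should give a floor that still holds when that loss occurs. Here the floor fails as soon as attrition passes 16%: 17% leaves 41.5 per arm, 18% leaves 41 and 20% leaves 40.

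Both power statements are attached to this retained number. If the rate and the number disagree, a reader cannot tell which one the power was computed at, and has to check whether each claim survives at the lower number.

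**Working it through.** **Step 1. Retained number.** Per arm: 100 / 2 = 50.

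- At 20% loss: 50 × (1 − 0.20) = 40 per arm, 80 in total.
- Loss implied by 42: 1 − 42/50 = 0.16.
- Recruitment needed to keep 42 at 20% loss: 42 / 0.80 = 52.5, so 53 per arm (106 dyads).

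One route does lead to 42: 50 / 1.2 = 41.7, the shortcut of inflating by (1 + d) run backwards. That is a possible origin only, and dividing by 1.2 is not a 20% loss.

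**Step 2. Power formula.** For a between-arm comparison averaged over m equally correlated measurements:

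λ = f² × N × m / [1 + (m − 1) × ρ], tested against F(1, N − 2)

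N is the total number retained and ρ = 0.22. Alpha = 0.05 two-sided is my assumption.

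**Step 3. Active phase.** Effect size: f = (10/30)/2 = 0.167, printed as 0.17. With m = 21 the denominator is 1 + 20 × 0.22 = 5.4.

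| Retained per arm | λ at f = 0.17 | Power, f = 0.17 | Power, f = 1/6 |
|---|---|---|---|
| 42 (N = 84) | 0.0289 × 84 × 21 / 5.4 = 9.44 | 85.9% | 84.5% |
| 40 (N = 80) | 0.0289 × 80 × 21 / 5.4 = 8.99 | 84.2% | 82.7% |

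A normal approximation for 10 min/d agrees. The SD of a participant's mean is 30 × √(5.4/21) = 15.2, which gives 85.4% at 42 per arm and 83.6% at 40. The plan's claim of at least 80% is reproduced at both numbers. The smallest number per arm that gives 80% is 36 at f = 0.17, or 38 at f = 1/6.

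**Step 4. Later phases.** The plan does not say which number of measurements applies. I use 35, the more favourable of its two figures. The denominator is 1 + 34 × 0.22 = 8.48.

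| Retained per arm | λ at f = 0.15 | Power, f = 0.15 | Power, f = 0.1549 |
|---|---|---|---|
| 42 (N = 84) | 0.0225 × 84 × 35 / 8.48 = 7.80 | 78.8% | 81.3% |
| 40 (N = 80) | 0.0225 × 80 × 35 / 8.48 = 7.43 | 76.8% | 79.4% |

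The normal approximation gives 79.8% and 77.8%. With 21 measurements the F-test figures are 76.4% and 74.3%. The value 0.1549 is close to the largest f that would still print as 0.15. At f = 0.15 exactly, 45 per arm are needed for 81%.

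**The case against.** The best case for the plan has four parts.

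**The rate is approximate.** It carries a tilde, and two dyads per arm is a small gap that loose rounding could explain. This stands as to size. It does not remove the mismatch, because 42 is given as a minimum and fails at any loss above 16%.

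**Power inputs are rounded or unstated.** An f just under 0.155 would print as 0.15 and gives 81.3% at 42 per arm, so the later-phase claim may have been correct as computed. This also stands, but only at 42. At 40 per arm the same f gives 79.4%.

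**Dropouts are not discarded.** FIML uses their partial data, so treating the information as exactly 40 per arm is a conservative convention. That is fair, and the restated text should say so. It does not change the retained number, which is a headcount and is the number the plan itself ties its power to. A participant who leaves before month 7 has no observations in the later phases.

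**The shortfall is mostly not due to this error.** At f = 0.15 the 81% is already missed at 42 per arm; going to 40 takes off about two more points. This is correct.

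A reader might also infer that one retained number cannot serve both 6 and 18 months, since the protocol's section on removal from the study lists events that accumulate. For example: "If an alternative caregiver cannot be identified the individual with AD will be censored from the study from that time forward". The documents do not support calling that an error. They give no removal rates and no period for the 20%, and a replacement caregiver is sought first. If 20% is an 18-month figure, using it at 6 months is cautious. Separate numbers would be a reporting preference.

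**Conclusion.** The inconsistency is real and minor: 20% attrition leaves 40 per arm, and 42 per arm is 16% attrition.

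- **Active phase.** The claim of at least 80% holds at either number.
- **Later phases.** The claim of at least 81% is not reproduced at f = 0.15 exactly (about 79% at 42 per arm, 77% at 40). It is reachable at 42 only with f near 0.155, and not at 40 with any f that rounds to 0.15.

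These power figures rest on an assumed two-sided alpha of 0.05, an equal correlation of 0.22 across measurements, 35 measurements for the later phases, and counting only retained participants. The retained-number arithmetic needs none of these.

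Two stronger readings should be resisted. A reader might infer that the primary comparison is underpowered; the figures show that it is not, even at 40 per arm. A reader might also infer that retention monitoring depends on the 42. The data and safety monitoring section lists accrual, adverse events, compliance and out-of-range laboratory data for review, and sets no retention threshold.

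A separate matter in the same paragraph is larger than the two-dyad gap. The example of 6 min/d with SD 30 gives f = (6/30)/2 = 0.10, not 0.15. The power figures above grant the plan its 0.15.

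**What to change.** In the sample size section, make the rate and the number agree. Either state at least 40 per arm after about 20% attrition, or state at least 42 per arm after about 16%.

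Then restate power for both phases at the chosen number, with alpha, sidedness, number of measurements and unrounded f:

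- **At 40 per arm:** about 83–84% for the active phase and about 77% for the later phases at f = 0.15.
- **At 42 per arm:** about 85–86% and about 79%. If the f actually used was nearer 0.155, give that value with the 81%.

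Add a sentence saying that the retained number is a headcount and that the FIML analysis also uses dropouts' partial data.

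The cost is wording only, with no extra participants and no change to design or analysis. The stated later-phase power becomes slightly less favourable.
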